687 used to secure the CGM sensor, or to secure the insulin infusion sets for the
688 Continuous Subcutaneous Insulin Infusion (CSII). If these reactions occur, different
689 adhesives or “under-taping” (such as with IV 3000, Tegaderm, etc.) will be tried,
690 sites will be rotated frequently, and a mild topical steroid cream or other medication
691 may be required.

692

693 Whenever the skin is broken there is the possibility of an infection. The CGM
694 sensor and insulin infusion set sites are inserted under the skin. It is possible that
695 any part that is inserted under the skin may cause an infection. These occur very
696 infrequently, but, if an infection was to occur, oral and/or topical antibiotics can be
697 used. The risk of skin problems could be greater if a sensor or infusion set is used
698 for extended periods of time. Therefore participants will be carefully instructed
699 about daily inspection of their sensor and infusion set sites.

700

701 Data downloaded from the CGM sensor, insulin pump, and the home glucose and
702 ketone meters will be collected for the study as measures of diabetes self-
703 management behaviors. Some people may be uncomfortable with the researchers'
704 having such detailed information about their daily diabetes habits.

705

706 **CHAPTER 5: MISCELLANEOUS CONSIDERATIONS**

707

708 **Potential Benefits**

709 Fiasp® may provide a more rapid onset of insulin action and improved post-prandial
710 glycemic control.

711

712 **Subject Compensation**

713 For Part 1, participants will be compensated \$50 for each visit, \$15 for completing
714 weekly uploads to Carelink for a maximum payment of \$245. For part 2, subject will
715 receive \$50 for each visit, and \$20 for uploading to Carelink and contact with the
716 investigators every two weeks they are in the extension phase. Maximum payment
717 of \$160. Compensation of partial participation will be prorated.

718

719 **Subject Withdrawal**

720 Participation in the study is voluntary, and a subject may withdraw at any time. The
721 investigator may withdraw a subject who is not complying with the protocol. For
722 subjects who withdraw, their data will be used up until the time of withdrawal.

723

724 **Subject Discontinuation Criteria**

725 Subjects who become pregnant will be discontinued from the study. The
726 investigator may withdraw a subject who is not complying with the protocol.
727 Withdrawal of a subject will be considered for the following reasons: 1) Failure to
728 monitor their sensor and infusion sites on a daily basis; 2) developing >1.0 mmol/L
729 ketones on 2 or more occasions and failing to change their infusion set or a single
730 episode of diabetic ketoacidosis due to an infusion site failure. For subjects who
731 withdraw or who are withdrawn, their data will be used for analysis purposes up until
732 the time of withdrawal.

733

734 **Confidentiality**

735 For security and confidentiality purposes, subjects will be assigned an identifier that
736 will be used instead of their name. De-identified subject information may also be
737 provided to Medtronic Diabetes.

738

739 **Level of Risk**

740 This research proposal in children is consistent with United States Department of
741 Health and Human Services, Protection of Human Subjects, Subpart D, Section
742 46.404 (Research not involving more than minimal risk).

743

744 **Planned Duration of the Entire Study**

745 Planned duration of the entire study will be 6 months.

747 **CHAPTER 6: STATISTICAL CONSIDERATIONS**

748

749 This is a pilot study to determine if there are any clinical issues with using Fiasp® in
750 the 670G hybrid closed-loop system. These studies are not statistically powered.

751

752 In the blinded cross-over studies (Part I) we will use data obtained during the
753 second week of each arm to compare the following measurements using a mixed-
754 effects model accounting for crossover study design of the study with the sequence
755 of treatment nested within the patient:

756

a) time in range (70-180 mg/dl)

757

b) percent time <70 mg/dl,

758

c) mean glucose,

759

d) glucose CV,

760

e) total daily insulin dose,

761

f) total daily basal insulin,

762

g) insulin delivery from MN to 6AM, and 6AM to MN

763

764 We will test to see if there is any difference in pharmacodynamics when using
765 Fiasp® in the home environment when they are eating their usual breakfast.

766

767 Insulin pharmacodynamics following the standard breakfast will be assessed by
768 measuring the peak glucose concentration (C_{max}), time to C_{max} (t_{max}), and estimated
769 average glucose excursions were assessed using sensor glucose values at a time
770 interval of 0 to 180 minutes after breakfast bolus. If a bolus was given between
771 120-180 minutes following the breakfast bolus, CGM values were only used up to
772 the time of the bolus. The glucose at the time of the breakfast bolus (Time 0) will be
773 set to 0 mg/dL for each meal, and the remaining CGM values were adjusted
774 proportionally to allow analysis of postprandial glucodynamic parameters. We will
775 utilize a mixed-effects model accounting for crossover study design of the study with
776 the sequence of treatment nested within the patient. Breakfast meals are excluded
777 from postprandial analysis if: 1) the rate of change was greater than 0.3mg/dL/min
778 in the 1 hour prior to breakfast, 2) subjects gave a subsequent bolus prior to 120
779 minutes following the breakfast bolus, or 3) subjects deviated from their typical
780 breakfast. Dinner meals will be assessed when there has been no additional food
781 intake after dinner. The duration of insulin delivery to cover the meal will be
782 determined by the time it takes the post prandial glucose to reach 160 mg/dL
783 beyond 1 hour of eating. The peak glucose will also be recorded.

783

784 During the 6 week optimization study (Part II) we will use data obtained during the
785 first two weeks of the study (before data was reviewed and changes made by the
786 investigators) to data obtained during the last two weeks of the 3 month optimization
787 period. We will compare the following measurements using paired t-tests for data
788 with a normal distribution and a Mann-Whitney rank sum test for data that is not
789 normally distributed:

790

a) time in range (70-180 mg/dl)

791

b) percent time <70 mg/dl,

792

c) mean glucose,

- 793 d) glucose CV,
- 794 e) total daily insulin dose,
- 795 f) total daily basal insulin,
- 796 g) insulin delivery form MN to 6AM, and 6AM to MN
- 797 h) CHO:I ratios at breakfast, lunch and dinner
- 798 i) Active insulin time
- 799 j) Number of days between infusion set changes
- 800 k) Erythema (mm) and induration (mm) at infusion sites when they are changed
- 801 l) Average daily insulin, and mean glucose for each day of infusion set wear
- 802 m) Number of episodes of unexplained hyperglycemia in the first month vrs the
- 803 last month
- 804
- 805
- 806
- 807

808 **CHAPTER 7: REFERENCES**

809

- 810 1. Heise T, Hovellmann U, Nosek L, Sassenfeld B, Thomsen KMD, Haahr H.
811 Pharmacokinetic Properties of Fast-acting Insulin Aspart Administered in Different
812 Subcutaneous Injection Regions: Response to the commentary by Nuggehally R. Srinivas.
813 Clinical drug investigation 2017.

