- 332 7. Usual carbohydrate intake is at least 60 grams a day, and willing to have at
333 least 25 grams of carbohydrates for breakfast
- 334 8. For females, not currently known to be pregnant
- 335 9. An understanding of and willingness to follow the protocol and sign the
336 informed consent
- 337 10. Willing to have photographs taken of their infusion sites
- 338 11. Willing to download their 670G pump every 1-2 weeks to a research Carelink
339 account
- 340 12. Willingness to answer a brief online questionnaire every 2 weeks
- 341 13. Must be able to understand spoken or written English
- 342 14. For subjects participating in Part 2 of this study they will need to be using
343 Fiasp® as part of their usual care
- 344 15. Hemoglobin A1c between 6 and 10% at the time of enrollment

345

346 **Exclusion Criteria**

347 The presence of any of the following is an exclusion for the study:

- 348 1. Pregnant or lactating females
- 349 2. No hypoglycemic seizure or loss of consciousness in the past 6 months
- 350 3. Severe episode of DKA in the 6 months prior to study enrollment that was
351 unrelated to an infusion set failure
- 352 4. No known cardiovascular events in the last 6 months
- 353 5. No active proliferative diabetic retinopathy

- 354 6. Known tape allergies
355 7. Current treatment for a seizure disorder
356 8. Cystic fibrosis
357 9. Active infection
358 10. A known medical condition that in the judgment of the investigator might
359 interfere with the completion of the protocol
360 11. Inpatient psychiatric treatment in the past 6 months
361 12. Presence of a known adrenal disorder
362 13. If on antihypertensive, thyroid, anti-depressant or lipid lowering
363 medication, with lack of stability on the medication for the past 2 months
364 prior to enrollment in the study
365 14. Abuse of alcohol
366 15. Dialysis or renal failure
367 16. Known eGFR <60%

368

369 Note: Adequately treated thyroid disease and celiac disease do not exclude
370 subjects from enrollment.

371

372 **Recruitment Plan:**

373 We will contact subjects at our clinic who are using the 670G system and are using
374 Novolog or Fiasp® insulin. A short description of the present study will be given to
375 them via email, phone or in-person. If the subject expresses interest, then the study
376 will be presented in detail. The goal will be to enroll four subjects each week to
377 establish cohorts of 4 subjects.

378

379 **Informed Consent Plan and HIPAA Authorizations:**

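### Exclusion items 2, 4 and 5 are worded as absences under a heading that excludes on presence, so the entry rule cannot be applied as written

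*Combined protocol and SAP*

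**What the plan says.** Chapter 2, Exclusion Criteria, gives one rule for the whole list: "The presence of any of the following is an exclusion for the study". Sixteen numbered items follow.

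Three of them begin with *No*:

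- Item 2: "No hypoglycemic seizure or loss of consciousness in the past 6 months"
- Item 4: "No known cardiovascular events in the last 6 months"
- Item 5: "No active proliferative diabetic retinopathy"

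The other 13 (items 1, 3 and 6 to 16) each describe something that excludes when it is present. Item 3 begins "Severe episode of DKA in the 6 months prior to study enrollment that was", and item 7 is "Current treatment for a seizure disorder".

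The separate eligibility list in the same chapter gives criteria that a subject must meet. It does not mention severe hypoglycemia, cardiovascular events or retinopathy. Visit 1 in Chapter 3 has the history record retinal and cardiac conditions but attaches no entry rule to them.

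**The concern.** The heading and the three items point in opposite directions. Under a rule that excludes on presence, an item beginning with *No* is satisfied by the subject who does not have the condition, and that subject is then excluded. The subject who has the condition does not trigger the item.

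What is at stake is whether the entry rule can be used. These three lines are the only explicit entry rule in the document on these three histories. Item 2 also bears on a risk that the plan itself discusses: Chapter 4 lists hypoglycemia after a meal bolus among the possible side effects, and Chapter 3 treats unconsciousness or seizure as a safety reason to change pump settings in the blinded phase. General Considerations in Chapter 1 commits the study to following the protocol, and a literal reading would put every ordinary enrolment in conflict with that commitment. The synopsis places the study at one institution, but Chapters 3 and 4 also refer to research sites and participating investigators in the plural, so more than one person may have to apply the list.

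**Working it through.** The plan gives no figure to reproduce here. The check is a logical one, done by hand.

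**Inputs** (all from Chapter 2, Exclusion Criteria)

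- Rule: a subject is excluded if at least one listed item is true of that subject.
- S = seizure or lost consciousness from hypoglycemia within the 6-month window (subject matter of item 2).
- C = known cardiovascular event within the 6-month window (item 4).
- R = active proliferative retinopathy (item 5).

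**Count of items.** 16 in total, 3 worded as absences, 16 − 3 = 13 worded as excluding conditions.

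**As written.** Item 2 is true when S is absent, item 4 when C is absent, item 5 when R is absent. So:

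excluded = (not S) or (not C) or (not R) = not (S and C and R).

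**With the three items worded as presences.**

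excluded = S or C or R.

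Three yes/no conditions give 2 × 2 × 2 = 8 combinations:

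| S | C | R | As written | Worded as presences |
|---|---|---|---|---|
| no | no | no | excluded | passes |
| yes | no | no | excluded | excluded |
| no | yes | no | excluded | excluded |
| no | no | yes | excluded | excluded |
| yes | yes | no | excluded | excluded |
| yes | no | yes | excluded | excluded |
| no | yes | yes | excluded | excluded |
| yes | yes | yes | passes | excluded |

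As written, 7 of 8 combinations are excluded and only the subject with all three conditions passes these items. Reworded, 7 of 8 are again excluded, but the one that passes is the subject with none. The two versions disagree in two rows: the ordinary candidate with none of the conditions, and the candidate with all three. They agree in the other six.

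**Can the heading be reread to rescue the three items?** If the list were taken as conditions to be met, items 2, 4 and 5 would read correctly, but the other 13 would be inverted: subjects would have to be pregnant or lactating, have cystic fibrosis, and so on. No single reading of the heading fits all 16 items.

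**Is the rule stated correctly elsewhere?** The eligibility list, the note after the exclusion list, the eligibility assessment paragraphs and Visit 1 do not restate any of the three items. Item 7 concerns treatment for a seizure disorder, which is not the same as a past hypoglycemic seizure. Item 10, beginning "A known medical condition that in the judgment of the investigator might", is discretionary and turns on whether a condition would get in the way of finishing the study.

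**The case against.** The strongest reply is that nobody would misread this. *No* can be taken as a prohibition, meaning that such a history is not allowed, and the neighbouring items on ketoacidosis, seizure treatment and renal failure show that the list is meant to keep higher-risk subjects out. The literal reading also defeats itself: it turns away the ordinary candidate, so a site applying it would notice at the first screening. There are partial backstops too. Item 10 leaves room for judgment, the Visit 1 history covers retinal and cardiac conditions, study personnel assess eligibility by history and examination, and recruitment is from the investigators' own clinic. Most of this stands. It makes actual harm unlikely, but it does not make the text right, and none of the backstops states the rule.

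Three stronger readings are tempting, and the document does not support them:

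- A reader might infer that the list as written lets high-risk subjects in. Item by item, a subject with the condition does escape that item. But any one item is enough to exclude, so a subject with one or two of the conditions is still caught by the remaining items. Only the subject with all three gets past them.
- A reader might infer that the study's main safety protection fails. The document does not rank eligibility above its other safeguards. Chapter 3 also provides weekly upload review for safety in Part 1, triggers for changing settings, and rules on ketones and infusion sets; Chapter 5 gives withdrawal criteria.
- A reader might infer that screening forms or deviation records are wrong as a result. The document shows no eligibility checklist and describes no deviation log, so this is at most a risk to be checked.

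**Conclusion.** The point holds as an internal contradiction in a stated entry rule. Three of 16 exclusion items run opposite to their heading. Applied literally, they reject 7 of 8 combinations of the three conditions, including the subject with none, and pass only the subject with all three. The 7 of 8 counts combinations, not people. The document gives no frequencies for these histories, so no share of candidates can be stated, and none is needed.

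The conclusion rests on reading the heading as it stands, with any one item sufficient to exclude, and on the absence of a correct restatement elsewhere. That the three items were meant as excluding conditions is an inference from the rest of the list. It is a safe one: absence wording is natural in an eligibility list, where criterion 8 already uses it for pregnancy, so misplaced inclusion-style text is the likely origin.

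There is no statistical consequence. Chapter 6 says "These studies are not statistically powered", and no endpoint, analysis or sample size depends on these lines. The correction should be made because a rule that gives the intended result only when its wording is set aside invites inconsistent screening.

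**What to change.** Reconcile items 2, 4 and 5 with the heading in one of two ways:

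1. Remove the leading *No* from each, so that it names the excluding condition as the other 13 items do; or
2. Move the three lines to the eligibility list, where their present wording reads correctly as a requirement to be met.

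Either way, check any screening form or case report form derived from the list against the corrected text.

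The cost is a wording amendment to three items, with whatever administrative review such a change needs, and one check of the form. It adds no procedure, visit, subject or analysis.

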243 optimization phase to assess if making changes to meal coverage with the
244 knowledge that Fiasp® is being used can optimize the advantages of the 670G
245 pump with Fiasp® use, and to observe longer term use of Fiasp® in the 670G
246 pump. This will be a 6 week study.

247

248 *Part 1: Randomized cross-over, blinded study which includes assessment of meal*
249 *pharmacodynamics.*

250 Part 1 will be a randomized cross-over blinded study and will also test to see how
251 the 670G pump responds to the introduction of Fiasp® insulin. Subjects enrolled in

252 the study will have a 2 week period of optimization with weekly assessments of their
253 Carelink download before entering the blinded phase of the study. They will use
254 their usual home insulin during the optimization phase. They will then be started
255 on their first blinded insulin (aspart or Fiasp®) which they will use for 2 weeks,
256 before they cross-over to the other insulin. During the second week of each arm we
257 will:

- 258 1) Assess CGM measurements of:
 - 259 a) time in range (70-180 mg/dl)
 - 260 b) percent time <70 mg/dl,
 - 261 c) mean glucose,
 - 262 d) glucose CV,
- 263 2) Pump data for:
 - 264 a) CHO:I ratios at Breakfast, Lunch and Dinner,
 - 265 b) total daily insulin dose,
 - 266 c) total daily basal insulin,
 - 267 d) insulin delivery from MN to 6AM, and 6AM to MN
- 268 3) We will test to see if there is any difference in pharmacodynamics when
269 using Fiasp® in the home environment when they are eating their usual
270 breakfast.
- 271 4) We will also assess their glucose levels following a high fat meal at dinner of
272 at least 30 grams of fat.

273

274 *Part II: Extended Use Observational Study.*

275 This study will consist of 6 weeks of closely monitored home use of the 670G pump
276 with review of their pump and sensor downloads every 2 weeks by clinicians who
277 are experienced in using the 670G pump. The goals of this phase of the study are
278 to:

- 279 1) Assess how Fiasp® changes meal bolusing, i.e. do adjustments need to be
280 made in their carbohydrate to insulin ratios or timing of their boluses when
281 they are using Fiasp® I
- 282 2) Assess how Fiasp® works with the higher fat meals that may occur with
283 dinner, i.e. will the dinner dose need to be divided into early and late boluses
- 284 3) Assess how Fiasp® affects infusion sites under usual care conditions, i.e are
285 there any local reactions to Fiasp®

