461 more than 10 mm of erythema or induration. They will be given a ruler for making
462 these measurements. If there is more than 3 mm of induration or redness they will
463 be asked to take a picture and enter these measurements into a text to the study

464 coordinator or submit the information directly into RedCap.

465

466 The goal will be to have sensor wear at least 80% of the time and in automode at
467 least 70% of the time. The pump will be uploaded to a research Carelink account
468 each week. While in the blinded phase of the study the clinical staff will refrain from
469 making changes to 670G pump settings unless requested by the subject or for
470 safety reasons such as an episode of severe hypoglycemia (unconsciousness or
471 seizure), >10% time <70 mg/dl, or >20% of the time over 250 mg/dl.

472

473 **Part 1: Randomized, cross-over, blinded study to assess any adaptations of**
474 **the 670G pump to Fiasp® and to assess meal pharmacodynamics of Fiasp®**
475 **compared to aspart with a typical breakfast in the home environment**

476

477 Participants will have a 2 week run-in on their usual home insulin (aspart of Fiasp®).
478 During the run-in, their pump will be downloaded weekly, reviewed by the clinical
479 staff and adjustments will be made to their settings as needed to optimize their
480 glycemic control. Participants will then be randomly assigned to 2 sequences of
481 testing starting with either aspart or Fiasp®. They will use each insulin for two
482 weeks. The participants and the investigators will be blinded to the insulin. During
483 the second week of using a blinded insulin they will have the meal
484 pharmacodynamics testing. They will then cross-over to the other insulin and
485 during the second week they will repeat meal pharmacodynamics testing. At the
486 end of each week they will upload their 670G pump to a Carelink clinical (research)
487 account and it will be reviewed by the research staff for safety purposes.

488

489 Procedure for meal testing. For each week of meal testing they will be asked to
490 have 3 days with a consistent breakfast that is the same for all 6 days they are
491 doing a meal test (3 days on each insulin). The breakfast studies should ideally
492 occur on standard work days (not holidays or weekends). On these three days they
493 will be asked to have a dinner with at least 30 grams of fat and no additional food in

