494 the evening (unless they are treating hypoglycemia). They will be asked to take a
495 picture of the dinner meal and identify their food and portion sizes. If they have a
496 smart phone (Android or Apple), they may download Calorie Mamma® or Calorie
497 King® to help them in calculating carbohydrates, protein and fat from the meal.
498 They will do this for each of their dinner meals on each of the days they are doing
499 the breakfast study, and for the breakfast meals they are eating each morning as
500 part of the pharmacodynamic testing. They will change their infusion set before
501 dinner prior to the first day of starting a standard breakfast, i.e., if they work from
502 Monday to Friday, this could be done on Sunday.

503

504 They are blinded to the insulin and the insulin dose decisions for these meals is also
505 not under their control since: 1) The overnight insulin delivery is not under their
506 control, 2) The timing of the meal bolus will be the same for all mornings, the dose
507 will be given immediately before eating, 3) Their dose of insulin will be determined
508 by their pump using their preset insulin-to-carbohydrate ratio and they will be eating
509 the same amount of carbohydrates each morning. They also will not be getting a

510 correction dose of insulin in the morning because they are using the closed-loop
511 controller overnight. If they required a correction dose of insulin, we will not use the
512 data from that morning in our data analysis. We will assess during each of these
513 four weeks the time in-range (70-180 mg/dl), mean glucose, CV, and time <70
514 mg/dl.

515

516 At the end of each two week period of blinded insulin use the participants and the
517 health care providers will be given a questionnaire asking them which insulin they
518 thought they were using, and if they had noticed any advantages to disadvantages
519 while they were using this insulin, and whether they would have wanted to make
520 any changes to their insulin delivery settings while using the insulin.

521

522

523 **Part 2: Extended Use Optimization Study**

524

525 To be eligible for Part 2 one of the inclusion criteria will be that the subject is
526 currently using Fiasp® insulin under their usual care. Subjects for Part 1 may
527 participate in part 2, and we will also recruit subjects outside of part 2 who are
528 currently using a 670G pump and taking Fiasp insulin. They will download their

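### Part 1 test dinners are not matched between insulins and their recorded content goes unused, which costs precision in the Fiasp–aspart dinner comparison

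*Combined protocol and SAP*

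**What the plan says.** Section 1.4 (Protocol Synopsis) lists the dinner response among the Part 1 assessments: "We will also assess their glucose levels following a high fat meal at dinner of" at least 30 g of fat.

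Chapter 3, Part 1, Procedure for meal testing, treats the two meals differently.

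- **Breakfast.** Subjects are to "have 3 days with a consistent breakfast that is the same for all 6 days they are" tested, three on each insulin. On dosing: "The timing of the meal bolus will be the same for all mornings". Carbohydrate is also held constant from one morning to the next.
- **Dinner, on the same days.** Subjects "will be asked to have a dinner with at least 30 grams of fat and no additional food in" the evening, except to treat hypoglycemia. There is no upper limit on fat, no carbohydrate or protein target, and no request to repeat a dinner across days or insulins.
- **Recording.** For each test dinner subjects take a "picture of the dinner meal and identify their food and portion sizes. If they have a" smart phone, they may use an app "to help them in calculating carbohydrates, protein and fat from the meal".

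Chapter 6 sets the breakfast glucose at bolus time to zero and excludes breakfasts that depart from the subject's usual one. Dinners are assessed when nothing was eaten afterwards. They are scored by the time for glucose to come to 160 mg/dL "beyond 1 hour of eating. The peak glucose will also be recorded". Neither measure is referenced to the starting glucose. No dinner model, covariate or content-based exclusion is given.

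**The concern.** Peak glucose and time to 160 mg/dL both respond to how much carbohydrate and fat was eaten. A subject could eat a modest dinner just above the fat minimum in one period and a much larger one in the other, and comply both times. The breakfast rules prevent this, but the dinner rules do not. The information that could correct for it is collected and then has no role in the analysis.

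The dinner response matters to the study's own questions. Chapter 4 (Potential Risks and Side Effects) names prolonged hyperglycemia after a high-fat meal as a risk, and Part 2 asks whether the dinner dose will need dividing. Part 2 has no aspart arm, so Part 1 is the only randomised Fiasp–aspart evidence on dinner that this study will produce. With at most 20 subjects, avoidable variation in that comparison is worth removing.

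**Working it through.** The plan has no figure to reproduce. Chapter 6 says the studies are not powered, and no SD, effect size or alpha is stated. The check asks how much precision unmatched dinners cost, and whether they bias the contrast.

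**Inputs from the documents.** n = 20 subjects (the stated maximum); k = 3 dinners per insulin.

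**Assumed inputs.**
- s_w, the residual SD of peak glucose with identical dinners: 40 mg/dL, range 25.9–48.8. The range is the spread of the Cmax SDs in Table 2 (Section 1.2.3). Those are baseline-referenced breakfast peaks from another study and are not within-subject dinner SDs, so they serve only as a guide to scale.
- s_m, the extra SD from differing dinner content: 20–40 mg/dL. Nothing in the documents supports a particular value.

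**Formula.** For the mean within-subject difference between insulins, SE = √[2(s_w² + s_m²)/(k·n)] = √[(s_w² + s_m²)/30]. The 95% half-width is t(19) × SE, with t(19) = 2.093.

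**With s_w = 40:**
- s_m = 0 (matched): √(1600/30) = 7.30; half-width 15.3 mg/dL.
- s_m = 20: √(2000/30) = 8.16; half-width 17.1, an increment of 1.8.
- s_m = 40: √(3200/30) = 10.33; half-width 21.6, an increment of 6.3.

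**Half-widths (mg/dL) across the residual range:**

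| s_w | s_m = 0 | s_m = 20 | s_m = 40 | Increment |
|---|---|---|---|---|
| 25.9 | 9.9 | 12.5 | 18.2 | 2.6–8.3 |
| 40 | 15.3 | 17.1 | 21.6 | 1.8–6.3 |
| 48.8 | 18.6 | 20.2 | 24.1 | 1.5–5.5 |

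In terms of information, at s_w = 40 the variance ratio is 2000/1600 = 1.25 or 3200/1600 = 2. Twenty subjects with unmatched dinners are then worth 20/1.25 = 16 or 20/2 = 10 with matched dinners.

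**Bias.** A simulation of 20,000 null trials (s_w = 40, s_m = 30, paired t-test) gave:

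| Dinner content | Mean error (mg/dL) | Rejection rate |
|---|---|---|
| Unrelated to insulin | 0.03 | 5.1% |
| Shifts with insulin, worth 5 mg/dL | 5.06 | 8.3% |
| Shifts with insulin, worth 10 mg/dL | 9.96 | 17.7% |
| Shifts with insulin, worth 20 mg/dL | 19.91 | 54.5% |

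Free choice therefore leaves the estimate unbiased and the test valid. Only a dependence of dinner content on insulin does harm of the second kind.

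**The case against.** A reader might infer that the dinner contrast is confounded with meal content. The documents do not support that. Chapter 3 randomises the order and blinds both participants and investigators, and nothing in the plan makes dinner choice depend on the insulin. The end-of-period questionnaire asks subjects which insulin they thought they had, so guessing is contemplated. A resulting shift in dinners remains a possibility, not a finding.

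A reader might also infer that the crossover's within-subject control is lost. It is reduced. Each subject remains their own control for stable characteristics. Pump settings are largely held during the blinded phase, and meal variation is averaged over three dinners per insulin.

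Nor should meal content be charged with its stand-alone half-width. With s_m = 20–40 that component is 2.093 × √(s_m²/30) = 7.6–15.3 mg/dL, but variances add, so the precision actually lost is the smaller increment.

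Three mitigating points stand. The 670G takes a carbohydrate estimate and a premeal bolus (Section 1.2.2), so differing carbohydrate is at least partly covered by differing insulin. Content is recorded, so balance could be checked even under the present design. Dinner is also a secondary item in an unpowered pilot: the Part 1 title names only breakfast, the Chapter 6 mixed-model list omits dinner, and no formal dinner test is written down. Freely chosen dinners also suit a home-use study.

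These points limit the severity. They do not explain why breakfast is standardised and dinner is not, or why recorded content has no analytic use.

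**Conclusion.** The point holds as one of precision and reporting. Test dinners have a fat minimum and a no-later-food rule, are not matched between insulins, and are analysed without their recorded content. The consequence is added noise and scope for chance imbalance. Systematic bias would need dinner choice to shift with the insulin.

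For peak glucose the cost is about 2–6 mg/dL on a 95% half-width of 15.3 mg/dL at an assumed residual SD of 40, or about 1.5–8 mg/dL across residual SDs of 25.9–48.8. This rests on an assumed meal-content SD of 20–40 mg/dL, 20 subjects each contributing three usable dinners per insulin, and repeated dinners removing the content component completely. Imperfect repetition would shrink the gain. The text on matching is clear; the size is illustrative. No figure was calculated for time to 160 mg/dL. This is a worthwhile, inexpensive improvement and not a flaw that invalidates Part 1.

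**What to change.** **Chapter 3, Procedure for meal testing.** Ask each subject to repeat on the second insulin the same three dinners, in food and portions, that they logged on the first. The photographs and food records already required can serve as the template.

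**Chapter 6, dinner analysis.**
- Compare peak glucose and time to 160 mg/dL between insulins within subject, by matched dinner.
- Tabulate logged carbohydrate and fat by insulin.
- Where dinners were not repeated, adjust for logged carbohydrate and fat, and show the unadjusted result alongside.
- Keep any adjustment for pre-dinner glucose to a sensitivity analysis. In the second week of a period that value is measured after the study insulin has acted, so adjusting for it could remove part of the insulin effect.

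**Cost.** One sentence of instruction and a short addition to the analysis text. The apps are optional, so staff may need to derive carbohydrate and fat from some food records. Subjects carry the small burden of repeating three dinners, and fewer kinds of dinner are studied.
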